#### **5.4 *Subject Demographic and Baseline Characteristics***

Subject demographic and baseline characteristics will be summarized for each treatment. Descriptive summaries will include the number of subjects, mean, standard deviation, median, minimum and maximum for continuous parameters, frequencies and percentages for categorical parameters.

#### **5.6 *Efficacy Analyses for Primary Aims***

The study (both PART-1 continuous and PART-2 pulse) will utilize a 2-phase sequential parallel design with 6 weeks treatment duration in each phase. Eligible patients will be randomized to two groups with a 1:2 ratio, to ensure adequate sample in phase 2 (week 6-12). Patients in the first group (TLT) will receive TLT (continuous in PART-1 and pulse in PART-2) at both phases (week 0-12). Patients in the second group (Sham) will receive sham at phase-1 and will undergo a 1:1 ratio randomization to either TLT or sham in phase-2 (week 6-12), respectively. Patient retention rates during phase-1 of the trial are assumed to be 76%, based on our earlier study ELATED-2. The treatment differences from phase-1 and phase-2 will be combined with equal weights to estimate the overall treatment effect.

For the primary efficacy analysis, all patients in phase 1 will be compared, together with sham non-responders from phase 2 (sham non-responders are defined as those patients who failed to achieve a 50% decrease in their QIDS-C score at visit 13).

A. Antidepressant effect of the TLT: To test the significance of the antidepressant effect of TLT (in both PART-1 and PART-2) we will use a T-test for mean differences of two related measures and will primarily look at QIDS-C and HAM-D 17 total score mean change on TLT and compare it with the QIDS-C and HAM-D 17 total score mean change on Sham, the significance will be set at a p-value  $\leq 0.05$ . The time-points to estimate the mean differences are baseline and week 6 for all subjects and for subjects non-responders to sham who are re-randomized also week 6 and week 12. Rates of responders according to the CGI-Improvement (score 1 or 2) will be estimated at week 6 and 12 of the study (no statistics planned). Both completer analysis and intent-to-treat analysis will be performed to analyze the severity of depression at endpoint. Patient attrition and dropouts

will be analyzed. Potential differences between treatment groups in dropouts will be examined with the Fisher's Exact test.

B. Tolerability of the TLT: The frequency and severity of the reported side-effects and adverse events with the TLT will be compared in the TLT vs. Sham group (Fisher's Exact Test), following the SPCD design. The corrective measures adopted by the clinicians will also be reported, as well as the clinical judgment on the likelihood of the association of the side effect/ adverse event with the TLT.

C. Cognitive Tasks Analyses:

The secondary efficacy variable is the effect of TLT on cognitive performance as measured by selected cognitive tasks. All analyses will be conducted in accordance with SPCD design.

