**Endpoints:**

**Safety** - The safety endpoints will evaluate the TLT and sham groups for differences in tolerability through 12 weeks of follow-up.

**Efficacy** - The efficacy endpoint will be the antidepressant effect of TLT through week 12, as assessed using the QIDS-C scale.

**Engagement of Neuro-Inflammation** – The effect of TLT on inflammation will be assessed at week 6 and 12 by measuring the plasma levels of IL6, TNF- $\alpha$ , IL-1 $\beta$  as primary cytokines (compared to baseline).

**Engagement of Cognitive circuitry** – The effect of TLT on cognition will be assessed at week 6 and 12 by measuring pattern recognition and cognition with emotional stimuli (compared to baseline).

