**Study Sponsor**

[name] PhD

Principal Investigator

Massachusetts General Hospital

[name]

The method and general statistical analytical procedure of study, sequential parallel comparison design, has been described in previously published materials. That being that subjects are allocated to receive either the active treatment or placebo in both phases, or receive placebo within the first phase then receive the active treatment in the second. Therefore, there will be three groups analyzed: Active-Active, Sham-Sham, and Sham-Active. Only those considered non-responders in the first phase are analyzed within the second phase, as it is hypothesized they have a reduced placebo response, or have not found the initial phase of the intervention effective (Fava et al. 2003).

Process of calculation has been described in the Statistical appendix of the reference above. That being:

"Assume that patients will be randomized into three groups, the first two groups will initially receive placebo, those patients that do not respond to placebo will receive placebo (group 1) or drug (group 2). The third group will initially receive drug. The proportions randomized to the three groups will be  $a$ ,  $a$  and  $1 - 2a$ .

Let  $p_1$ ,  $q_1$  be the response rates to the first administration of drug and placebo respectively and let  $p_2$ ,  $q_2$  by the responses to the second treatment. To analyze these data we use a statistic based on  $h = w(p_1 - q_1) + (1 - w)(p_2 - q_2)$ . The weight,  $w$  and the randomization fraction,  $a$  are chosen to maximize the power of the test, based on the alternative hypothesis.

The standard error for  $h$  requires a special formula because some of the same patients who are included in the estimation of  $p_2$ ,  $q_2$  are included in the estimation of  $p_1$ ,  $q_1$ . The delta method was used to compute the standard error of  $h$ ...

Then

$$h = w \left( \frac{n_{3,1}}{n(1 - 2a)} - \frac{(n_{1,3} + n_{2,3})}{2na} \right) + (1 - w) \left( \frac{n_{2,1}}{n_{2,1} + n_{2,2}} - \frac{n_{1,1}}{n_{1,1} + n_{1,2}} \right)$$

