### **Primary Analysis**

QIDS: The changes in QIDS scores and the response rates, which was defined as 50% or more drop in QIDS score, are the two main output measures of the current study. All statistical analyses are performed on R software version 3.6.2 (R Core Team, 2019) with SPCDAnalyze package version 0.1.0 (Schoenfeld 2019). The package uses constrained longitudinal data analysis model. The level of statistical significance was set at  $p \leq 0.05$ .

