### **Secondary Analysis:**

HAMD: Secondary outcome measure was change in HAM-D scores and response rate defined as 50% or more drop in HAMD score. All statistical analyses performed R software version 3.6.2 (R Core Team, 2019) with SPCDAnalyze package version 0.1.0 (Schoenfeld 2019). The package uses constrained longitudinal data analysis model. The level of statistical significance was set at  $p \leq 0.05$ .

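### Protocol 5.6 and the SAP describe different primary analyses, and neither document says which one governs

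*Protocol*

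**What the plan says.** **Protocol, section 5.6.** On the test and outcomes: "we will use a T-test for mean differences of two related measures and will primarily look at QIDS-C and HAM-D 17 total score". The sentence goes on to compare mean change on TLT with mean change on sham at p ≤ 0.05. The time-points are baseline and week 6 for everyone, and weeks 6 and 12 for re-randomised sham non-responders. On weighting: "The treatment differences from phase-1 and phase-2 will be combined with equal weights to estimate the overall treatment effect". The only response rate in the efficacy comparison is the CGI-Improvement rate, which is to be estimated without a test. Hypothesis 1 in section 5.2 names the same pair of scales. The Study Summary, under Endpoints, is narrower: "The efficacy endpoint will be the antidepressant effect of TLT through week 12, as assessed using the QIDS-C scale".

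**SAP.** Under Primary Analysis, QIDS change and QIDS response (a fall of at least half) "are the two main output measures of the current study". The software is SPCDAnalyze, and "The package uses constrained longitudinal data analysis model". Under Secondary Analysis: "Secondary outcome measure was change in HAM-D scores and response rate defined as 50% or more drop in HAMD score". The SAP gives no phase weight for this trial. Its opening section reproduces a published appendix in which the weight and the randomisation fraction "are chosen to maximize the power of the test, based on the alternative hypothesis". That appendix concerns a binary outcome: p1 and q1 are to "be the response rates to the first administration of drug and placebo respectively".

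**The concern.** The estimate and its p-value depend on the model, the outcome and the phase weight. The two documents differ on the first two, and the SAP does not confirm the third. With no rule of precedence, the primary result could be chosen from several candidates after the data are seen. Each part is small (24 and 26 randomised), so reasonable choices can give different verdicts.

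The protocol's test also has a wording fault of its own. A related-measures t-test needs pairs, and TLT and sham patients are not paired.

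**Working it through.** **1. The two plans side by side**

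| Element | Protocol 5.6 | SAP |
|---|---|---|
| Test | t-test, related measures | constrained longitudinal model |
| Main outcomes | QIDS-C change, HAM-D17 change | QIDS change, QIDS response |
| HAM-D17 change | primary | secondary |
| QIDS response | defines sham non-response only | main measure, tested at 0.05 |
| Phase weight | equal, so w = 0.5 | none stated; a quoted generic rule |

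The only outcome in both lists is QIDS change.

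**2. The wording of the test.** Section 5.3 expects 16 sham and 8 active patients in phase 1 of PART-1, then about 5 and 4 in phase 2. Within each phase these are different people. The only pairs are a patient's own scores at the start and end of a phase, so a literal related-measures test would assess change within an arm. The rest of the sentence and its time-points suggest change scores compared between arms.

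**3. Which weights the quoted rule could give.** Neither document gives a figure here, so there is none to reproduce. Inputs: n = 24 and a = 1/3 (8/8/8); q1 = 0.30 from the 70% sham non-response in 5.3; the other rates are assumed and dropout is ignored. The SAP's standard-error expression, as printed, carries no n, so it was divided by 24 under the root. Power is Φ(z − 1.96). Over eight assumed sets (p1, q1, p2, q2) the optimal w runs from 0.41 to 0.66. Examples:
- (0.5, 0.3, 0.5, 0.1): optimal w = 0.41, power 46.8% against 45.7% at w = 0.5.
- (0.6, 0.3, 0.5, 0.1): optimal w = 0.51, power 58.4% at both.
- (0.7, 0.3, 0.7, 0.3): optimal w = 0.66, power 70.2% against 65.7%.

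So the rule does not fix one weight, and w = 0.5 costs between 0 and about 4.5 power points.

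**4. Effect of the weight on a change score (illustration only).** No QIDS SD is given, so the ELATED-2 HAM-D17 SDs in section 3.1 stand in: √((7.5² + 7.0²)/2) = 7.25. Phases are taken as independent.
- Estimate = w·Δ1 + (1 − w)·Δ2
- SE = 7.25·√(w²·V1 + (1 − w)²·V2), with V1 = 1/8 + 1/16 = 0.1875 and V2 = 1/4 + 1/5 = 0.45
- SE = 2.894 at w = 0.5 and 2.651 at w = 0.66

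| Assumed Δ1, Δ2 | w = 0.5 | w = 0.66 |
|---|---|---|
| 7.5, 3 | 5.25, z = 1.81, p = 0.070 | 5.97, z = 2.25, p = 0.024 |
| 3, 10 | 6.50, z = 2.25, p = 0.025 | 5.38, z = 2.03, p = 0.042 |
| 6.4, 6.4 | 6.40, z = 2.21, p = 0.027 | 6.40, z = 2.41, p = 0.016 |

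The difference of 6.4 is the ELATED-2 one (11.7 − 5.3). With it in both phases, the normal-test p is 0.042 at w = 0.41 and 0.015 at w = 0.706 (the variance-minimising weight, 0.45/0.6375).

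**5. Sensitivity.** With t on 22 + 7 = 29 df:
- Effects 7.5 and 3: 0.080 against 0.032.
- Effects 3 and 10: 0.032 against 0.052, but 0.049 at w = 0.65.
- Effects of 6.4 in both phases: 0.051 at w = 0.41.

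With 12/6 in phase 1 after 76% retention, V1 = 1/6 + 1/12 = 0.25, and SE is 3.033 at w = 0.5 and 2.908 at w = 0.66. On 23 df:
- Effects 7.5 and 3: 0.097 against 0.052.
- Effects 3 and 10: 0.043 against 0.077.

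**6. Patients in both phases.** At (0.6, 0.3, 0.5, 0.1) and w = 0.5, the sum of two independent phase variances is 0.25·(0.24/8 + 0.21/16) + 0.25·(0.25 + 0.09)/5.6 = 0.0108 + 0.0152 = 0.0260, so SE = 0.161. The SAP's printed expression also gives 0.161. The two agree to three decimals in all eight sets.

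**The case against.** The case for leaving this alone is that a SAP may refine a protocol, that 5.6 plausibly means change scores compared between arms, and that equal weights stand uncontradicted. Much of that is right about the weight. A reader might infer that the SAP adopts a rival, power-maximising weight. It does not: that text sits inside a quotation about response rates, is not tied to the longitudinal model, and comes with no alternative rates. The SAP is silent on its own weight.

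Three other stronger readings also fail.
- **That the weight can reverse the verdict in either direction at the planned counts.** With 16/8 then 5/4, effects of 3 and 10 stay below 0.05 on the normal test at w = 0.66 and only just pass it on 29 df. A clear crossing needs w = 0.706, which neither document gives, or the smaller 12/6 sample.
- **That section 5.6 miscalculates the standard error because some sham patients enter both phases.** It does not say how they are handled, but no harm is shown: for response rates the SAP's formula equals the independent-phase sum. For change scores independence is only assumed here.
- **That the SAP was written after unblinding, because part of it is in the past tense.** The documents do not establish when it was written relative to unblinding.

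The illustration models neither planned analysis and says nothing about the differences in test and outcome. Those rest on the text alone. They still stand, since the SAP announces no change from the protocol and gives no reason for one.

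**Conclusion.** The plan is wrong as written. The protocol and the SAP name different tests and different primary outcomes, and no sentence settles precedence. This rests on the text and needs no assumption. The related-measures wording must be corrected on either reading, and the SAP should confirm the protocol's equal weights, which are defensible in themselves.

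The size of the weight problem is modest and conditional. Against the quoted rule, w = 0.5 costs at most about 4.5 power points under the assumed rates. A change of verdict appears in some assumed cases and not in others, and it depends on the effect pair, the retained sample and the reference distribution. The study is described as a feasibility study, but it still plans tests at 0.05 with a power claim, so this should be corrected.

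**What to change.** Make one aligned edit before unblinding, or as a dated clarification if unblinding has already occurred.

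- **Protocol 5.6:** replace the related-measures t-test with the SAP's constrained longitudinal analysis for the sequential parallel design, applied to QIDS-C change as the single primary outcome. List HAM-D17 change and QIDS response as secondary.
- **SAP, Primary Analysis:** name QIDS-C change as the only primary outcome and move QIDS response to the secondary section. Add a sentence such as: *The phase 1 and phase 2 effects each receive weight 0.5, following protocol 5.6; the power-maximising choice in the quoted appendix is not used.*
- **Protocol 5.3:** state that the power figure uses ELATED-2, whose effect is reported in section 3.1 only on HAM-D17, and that no QIDS-C effect or SD is given.

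The cost is a few sentences, with no change to design, planned numbers or the protocol's weight. HAM-D17 change and QIDS response lose primary status, and the power claim is left without a stated QIDS-C basis until one is supplied.

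Keeping w = 0.5 can also cost power on a change score. With d = 6.4/7.25 = 0.88 in both phases and 16/8 then 5/4, power is Φ(0.882/0.399 − 1.96) = 59.9%, against 67.9% at w = 0.706. If the phase 2 effect is twice as large, w = 0.5 does better (91.2% against 88.1%).

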### **5.7 Safety Analyses**

The number and percent of Adverse Events through study completion will be presented for each treatment group by adverse event type.

### **5.8 Additional Safety Analyses**

Descriptive statistics for safety endpoints for each treatment group will include number of subjects, mean, standard deviation, median minimum and maximum for continuous variables, and frequencies and percentages for categorical variables.

## 6 Ethical Review & Regulatory Considerations

### 6.1 *Ethical Review*

Prior to the start of the study the Investigator will obtain IRB approval of the protocol and the Informed Consent Form. Additional documentation may be required pending applicable local requirements. At least the following documentation must be obtained:

- 1.The IRB/EC approval of the protocol.
- 2.The IRB/EC approval of the Informed Consent Form.
- 3.The IRB/EC annual (or any other frequency when applicable – i.e. quarterly, semiannually according to the local IRB/EC standard operating procedure) renewed approval of the protocol.
- 4.The IRB/EC approval of any revisions to the Informed Consent Form or amendments to the protocol.

### 6.2 *Regulatory Considerations*

This study will be conducted in accordance with the Good Clinical Practice (GCP) guidelines and other applicable regulatory requirements including but not limited to:

- The Food and Drug Administration (FDA) Regulations on Investigational Device Exemption (21 CFR 812),
- The FDA Regulations on research with human beings (21 CFR 50, 54 and 56),
- The Health and Human Services (DHHS) Regulations on research with human beings (45 CFR 46 Subparts A, B, C, and D) and
- The International Conference on Harmonization (ICH) “Guidance for Industry-E6 Good Clinical Practice: Consolidated Guideline.”

The Study will be conducted in the US in accordance with the Privacy Rule (45 CFR Parts 160 and 164) of the Health Insurance Portability and Accountability Act of 1996 (HIPAA).

### 6.3 *Monitoring Procedures*

Monitoring will be conducted by the PI who will periodically review lab results and clinical information. The PI will be coordinating the different phases of the protocol implementation such as TLT delivery and follow up. The PI will be frequently in contact with the other staff members responsible for TLT delivery and with Litecure Inc, which will lend the TLT device. We have minimized risks potentially associated with the use of Transcranial Light Therapy (TLT) by requiring two methods of contraception (although TLT has not been associated with teratogenic effect). In addition, we are providing the subjects with safety goggles or eye pads during the TLT delivery. We have also included treatment discontinuation rules based on the development of skin erythema, or discomfort

lasting more than 24 hours at the sites of TLT delivery (to prevent risk of subject's having an unknown skin photosensitivity).

Treatment will end for participants who experience temporary pain or discomfort during a treatment session. A research assistant or the study doctor will follow-up within a 24-hour period, after the discontinued treatment, with the patient who experienced discomfort. The subject may continue with the study if the acute pain stopped. If the subject experiences discomfort after 24-hours the aforementioned treatment discontinuation process may begin (e.g., Section 4.19.1, p. 29).

### **6.3.1 Training of study site personnel**

Training will be initiated prior to the protocol being implemented. Training will consist of both lecture and practicum. Application of TLT procedure will be performed only by PI or his/her designee trained by the Sponsor (or its designee) to perform the procedure.

## **6.4 Informed Consent**

The Principal Investigator will be responsible for developing the Informed Consent Form. The Informed Consent Form will be prepared in accordance with FDA 21 CFR Part 50 for all US sites. The Informed Consent Form will be used to explain in simple terms, before the subject is entered into the study, the possible risks and benefits to the subject. The Informed Consent Form will contain a statement that the consent is freely given, that the subject is aware of the risks and benefits of entering the study, and that the subject is free to withdraw from the study at any time.

Prior to a subject's participation in the study, the written Informed Consent Form will be signed and personally dated by the subject or by an individual authorized to sign on behalf of the subject per compliance with local regulations.

If a subject is unable to read or if a legal representative is unable to read, an impartial witness will be present during the entire Informed Consent Form discussion. After the written Informed Consent Form and any other written information to be provided to the subject is read and explained to the subject or legal representative, and oral consent to the subject's participation in the study has been given by the subject, the witness will sign and date the Consent Form.

A witness in the consent process is considered to be an individual that is impartial and independent of the study.

**Note:** *The Investigator must document acquisition of the written Informed Consent Form in the subject's medical records, and the subject or legal representative must be given a copy of the Informed Consent Form document prior to enrollment into the study.*

**6.5 Protocol Adherence**

The protocol must be read and followed by all participating study personnel.

**6.6 Data Collection**

Data will be captured on Case Report Forms - RedCAP. For each subject, a study binder will be kept locked in the MGH and NYUSOM site.

**6.7 Record Retention**

The Investigator must maintain a file of all documents and records relating to the conduct of the study. Subject files and other source data must be kept for the maximum period of time permitted by the hospital, institution or private practice, or as specified below.

Study records are subject to inspection by the FDA and other regulatory agencies.

**6.8 ClinicalTrials.gov**

ELATED-3 study will be registered with and posted on ClinicalTrials.gov ([www.clinicaltrials.gov](http://www.clinicaltrials.gov)).

### Table of Assessments

Week	Screening Visit	Treatment Visits																								Follow-Up Visits		
	0	1	2	3	4	5	6	7	8	9	10	11	12	13														
Visit	V0	V1	V2	V3	V4	V5	V6	V7	V8	V9	V10	V11	V12	V13	V14	V15	V16	V17	V18	V19	V20	V21	V22	V23	V24	V25		
PROCEDURES																												
Consent	Δ																											
MINI	Δ																											
ATRQ	Δ																											
HAM-D 17	Δ	Δ						Δ					Δ						Δ								Δ	
QIDS-C	Δ	Δ		Δ		Δ		Δ		Δ		Δ		Δ		Δ		Δ		Δ		Δ		Δ		Δ		
CGI	Δ	Δ		Δ		Δ		Δ		Δ		Δ		Δ		Δ		Δ		Δ		Δ		Δ		Δ		
MoCA	Δ																											
C-SSRS	Δ	Δ		Δ		Δ		Δ		Δ		Δ		Δ		Δ		Δ		Δ		Δ		Δ		Δ		
CADSS		Δ											Δ														Δ	
TLT/Sham Treatment		Δ	Δ	Δ	Δ	Δ	Δ	Δ	Δ	Δ	Δ	Δ	Δ	Δ	Δ	Δ	Δ	Δ	Δ	Δ	Δ	Δ	Δ	Δ	Δ	Δ		
PBQ-CR											Δ												Δ					
Physical Exam	Δ																											
Adverse Events Form		Δ		Δ		Δ		Δ		Δ		Δ		Δ		Δ		Δ		Δ		Δ		Δ		Δ		
Concomitant Medications	Δ	Δ		Δ		Δ		Δ		Δ		Δ		Δ		Δ		Δ		Δ		Δ		Δ		Δ		
Progress Note		Δ	Δ	Δ	Δ	Δ	Δ	Δ	Δ	Δ	Δ	Δ	Δ	Δ	Δ	Δ	Δ	Δ	Δ	Δ	Δ	Δ	Δ	Δ	Δ	Δ		
Vital Signs	█												█														█	
Laboratory	█																											
Cytokine Blood Draws	█												█														█	
MSIT		█						█					█						█								█	
Voice Pattern		█						█					█						█								█	
MST		█						█					█						█								█	
SDQ	▼	▼		▼		▼		▼		▼		▼		▼		▼		▼		▼		▼		▼		▼		
ASQ	▼	▼		▼		▼		▼		▼		▼		▼		▼		▼		▼		▼		▼		▼		
SAFTEE-SI		▼		▼		▼		▼		▼		▼		▼		▼		▼		▼		▼		▼		▼		
NEURO-QOL		▼		▼		▼		▼		▼		▼		▼		▼		▼		▼		▼		▼		▼		
MGH SFI		▼		▼		▼		▼		▼		▼		▼		▼		▼		▼		▼		▼		▼		
PBQ-SR											▼											▼						
TSRQ											▼												▼					
PEG		▼									▼												▼					

Δ Clinician Rated

█ Conducted by Research Coordinator

▼ Subject Rated

The CGI improvement scale is unmeasured on Visit 0 (screening visit).
